### **3.2 Allocation to Treatment Groups and Blinding**

Not applicable. The CEUS scan will be interpreted by the sponsor-investigator only.

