### Study Interventions and Measures:

Contrast-enhanced ultrasound scan with a duration of approximately 20 minutes. Qualitative analysis with visual assessment and quantitative analysis of the acquired scans will be performed by the sponsor-investigator. The scans will be assessed for diagnostic quality of images, artifacts encountered, and the presence of additional contributory diagnostic information.

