#### Qualitative analysis

Visual rating by 2 teams consisting of primary investigator and second radiologist (co-investigator). Each scan will be rated for diagnostic quality and qualitative rating of bowel perfusion. The visual rating scale used will be: 0 (absent flow), 1 (decreased flow), 2 (normal flow), 3 (increased flow).

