#### Quantitative analysis

Qontrast (Bracco Diag Inc., 510K regulatory status granted in 2004) contrast quantification software or similar software will be used to analyze the obtained CEUS scans. For each scan, wash-in and wash-out curves will be generated to quantify the rate of wash-in, time to peak intensity, peak intensity, and area under the curve.

The CEUS scans will be interpreted by the sponsor-investigator, and a second interpretation by a “second reader” in Radiology, who is part of a group of radiologists with sufficient training and expertise to read CEUS scans.

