## **6 STATISTICAL CONSIDERATIONS**

Up to 100 evaluable patients should be adequate for assessment of clinical feasibility and optimization of protocol. Qualitative analysis will be used as detailed above.

Quantitative analysis will be performed by drawing a region of interest in bowel segments and compared to control subjects (those with suspected or at risk of necrotizing enterocolitis but turns out to be normal on imaging and clinical evaluation) using non-parametric Wilcoxon testing.

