### **6.1 Primary Endpoint**

The primary objective of this study is to evaluate whether CEUS technique can be utilized to detect early alterations in bowel perfusion in NEC. The differences in bowel perfusion between normal subjects (those with suspected or at risk of necrotizing enterocolitis but turn out to be normal on imaging and clinical evaluation) versus NEC patients will be assessed qualitatively and quantitatively using the CEUS technique, as detailed above.

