## 6.2 Secondary Endpoints

Diagnostic quality of the CEUS exams will be evaluated with the scoring system of non-diagnostic (1), moderate artifacts degrading diagnostic quality (2), mild artifacts without degradation of diagnostic quality (3), and diagnostic (4). As a gold standard for NEC diagnosis, surgical findings (in those subjects undergoing surgery as part of clinical care) or Bell's staging criteria for NEC in combination with radiographic and clinical signs (for subjects not undergoing surgery) will be used.

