## 6.4 Sample Size and Power

As noted in the main text, no previous study has used contrast ultrasound to examine bowel wall perfusion. For power analyses, estimates of group differences were obtained from a study that provided mean perfusion values for a control group using Doppler ultrasound. Although contrast ultrasound and Doppler ultrasound rely on different methods to quantify perfusion (contrast quantifies by absolute intensity and Doppler quantifies by counting the color signal) the methods are similar enough that Doppler findings can inform the present study (and of note, given that contrast ultrasound is more sensitive, power analysis based on the Doppler findings are considered to be conservative). Given the reported bowel perfusion mean and standard deviation value for controls of 3.78 (SD = 1.1) [1], assuming a moderate effect (Cohen's D = 0.71), a sample size of 40 per group would provide power = 0.88 (alpha = 0.05). Since each subject has a clinical care US (control group) followed by a research CEUS (experimental group), each subject will serve as its own control. Since the CEUS method has not been applied to NEC imaging before, an interim statistical analysis may be considered to review image quality and comparisons between the results of each subject's CEUS scans and any available clinical US exams, to better inform the number of subjects required for statistical significance.

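### The plan contradicts itself on who reads the CEUS scans, and neither masks a reader nor sets one region-of-interest rule for the NEC-versus-control comparison

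*Combined protocol and SAP*

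**What the plan says.** **Who reads.** Section 3.2, the only section headed as dealing with blinding, reads in full: "Not applicable. The CEUS scan will be interpreted by the sponsor-investigator only". The Abstract says: "Qualitative analysis with visual assessment and quantitative analysis of the acquired scans will be performed by the sponsor-investigator". It names nobody else, but does not say that nobody else may read. Section 5 differs twice. Its qualitative part begins "Visual rating by 2 teams consisting of primary investigator and second radiologist (co-investigator", and its quantitative part says "The CEUS scans will be interpreted by the sponsor-investigator, and a second interpretation by a" further radiologist from a trained group.

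**What is read.** Section 5 defines a visual flow scale from 0 (absent) to 3 (increased) and four wash-in/wash-out curve parameters produced by software. Section 6 describes the quantitative step as "drawing a region of interest in bowel segments and compared to control subjects", tested with a Wilcoxon test. That phrase is the whole of the ROI instruction.

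**What is compared.** Section 6.1 sets NEC patients against normal subjects, defined as "those with suspected or at risk of necrotizing enterocolitis but turn out to be normal on imaging and clinical evaluation", both qualitatively and quantitatively.

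**What the team may know.** Section 3.1 admits infants whose NEC is already diagnosed. Under Sections 3.1.1 and 4.1, records are reviewed, the principal investigator talks with the referring neonatologist, and the study team discusses the case, all before the scan. Section 4.5.2 lists clinical diagnosis, surgical history and pathology among the data collected.

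**The concern.** In an open-label study without arms, blinding to treatment has no meaning, and Section 3.2 is right to that extent. Masking the person who reads the images is a different matter. Here it bears on the primary comparison, because both measurements depend on judgement: one is a visual grade, and the other starts from a choice of where in the bowel to draw.

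A reader who knows that an infant has NEC may grade borderline flow lower, or may look for the worst segment, while sampling an unremarkable segment in a control. The Wilcoxon test cannot separate such a reading difference from a perfusion difference. The contradiction about readers makes this worse: a site that follows Section 3.2 literally has one reader, who is also the sponsor-investigator, and no second read to compare with.

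**Working it through.** **1. The passages side by side**

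| Question | Section 3.2 | Abstract | Section 5 | Section 6 / 6.1 |
|---|---|---|---|---|
| Who reads | Sponsor-investigator only | Sponsor-investigator; others not excluded | Sponsor-investigator plus a second radiologist | Silent |
| Masked to status? | Not applicable | Silent | Silent | Silent |
| Read before or after the final label? | Silent | Silent | Silent | Silent |
| Same ROI rule in both groups? | Silent | Silent | Silent | Silent |

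The direct conflict is between Section 3.2 and Section 5.

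**2. The plan's own figure.** Section 6.4 states that, at Cohen's d = 0.71 and alpha = 0.05, "a sample size of 40 per group would provide power = 0.88". A two-sided two-sample t-test with d = 0.71 and n = 40 per group gives 0.880, so the figure reproduces for two independent groups. By normal approximation: 0.71 × √(40/2) = 3.175, and Φ(3.175 − 1.960) = 0.888. At the quoted SD of 1.1, the planned difference is 0.71 × 1.1 = 0.78 units.

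**3. What a reading shift would do.** The inputs are 40 per group (Section 6.4), the Wilcoxon test (Section 6), two-sided 5%, and no true difference. The shift b is an *assumption*. By normal approximation, the false-positive rate is Φ(b√20 − 1.960) + Φ(−b√20 − 1.960).

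| Shift b, all NEC infants, one direction | b√20 | Normal approximation | Wilcoxon, 20,000 simulated trials |
|---|---|---|---|
| 0 | 0 | 5% | 5% |
| 0.2 SD (0.22 units) | 0.894 | 15% | 14% |
| 0.3 SD (0.33 units) | 1.342 | 27% | 25% |

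Shifts of 0.2 and 0.3 SD are 0.2/0.71 = 28% and 0.3/0.71 = 42% of the planned effect.

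**4. When only some infants are affected.** A 0.5 SD shift in a quarter of NEC infants averages 0.25 × 0.5 = 0.125 SD. Simulated false positives are 8%; with a tenth of infants affected, 5%.

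**5. Segment selection.** Assume three segments per infant with within-infant correlation 0.5. The expected minimum of three standard normals is −0.846, so always taking the lowest segment shifts the value by 0.846 × √0.5 = 0.60 SD. Done in half of the NEC infants and in no control, the average shift is 0.30 SD.

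| Assumed selection | False positives |
|---|---|
| Lowest segment, half of NEC infants, no control | 26% |
| Same half, selection split 50/50 between lowest and highest | 5% |
| Same half, split 70/30 | 8% |
| Lowest segment in every infant of both groups | 5% |

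The last row is why one rule for both groups matters more than which rule is chosen.

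**The case against.** Several points on the other side are fair.

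- **Feasibility aim.** The Abstract and Section 6 speak of feasibility and optimisation, and Section 2.2 makes standardising the quantification a secondary objective. An ROI rule left open at the start is therefore partly intended. That stands, but it is no reason to leave the rule open when the two groups are compared.
- **Section 6.4 is mixed support.** Its 40 per group reproduces as two independent groups, but the same section says that each infant is its own control (clinical ultrasound against CEUS). The NEC-versus-control comparison rests on Sections 6 and 6.1.
- **Every bias figure is assumed.** Nothing in the plan suggests that readers pick the lowest segment, or that error runs one way; the flow scale also allows increased flow. The benign rows above belong to the answer as much as the 14% to 25%. The plan expects 100 evaluable subjects without giving the group split, so 40/40 is itself illustrative.
- **It can be repaired later.** Images are reviewable from the PACS (Section 4.5.3), so a masked re-read remains possible. The plan does not call for one, and a reading rule chosen after the results are seen is weaker.

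A reader might also infer that the readers do know the final group. The documents do not say so: they show access to clinical status, and for infants who are only suspected the final group is not yet known at screening. Because reading times are not fixed, this is not a safeguard either.

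**Conclusion.** The concern holds as a contradiction plus an omission. Section 3.2 and Section 5 cannot both stand on who reads, and no section masks the reading, times it or gives it a common ROI rule. An avoidable reading bias in the primary comparison is therefore left open.

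Its size cannot be taken from the documents. With 40 per group, no true difference and a one-directional shift of 0.2 to 0.3 SD in all NEC infants, false positives would be about 14% to 25%. They would be near 5% to 8% if few infants are affected or selection is roughly balanced. Confidence is high for the gaps in the text, not for any of these figures.

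Two stronger readings are not supported. The Abstract does not declare a sole reader; only Section 3.2 does. And although controls must be normal on imaging without an explicit exclusion of the study CEUS, Section 6.2 gives a diagnostic standard that does not list CEUS, so the text does not show that CEUS decides the group. That wording is a separate clarification.

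This is a cheap improvement, not a fatal flaw.

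**What to change.** 1. Reconcile the Abstract, Section 3.2 and Section 5 on who reads. The sponsor states which version stands.
2. State that perfusion ratings and ROI placement for the group comparison are done on de-identified clips in random order, without diagnosis, radiographs, surgical findings or pathology. If two readers stand and the sponsor-investigator cannot be masked, use the already planned second reader's masked read for the primary comparison.
3. Fix one ROI rule, identical in NEC and control infants, before the groups are compared. The choice of segments stays with the sponsor and may be settled on early scans under the secondary objective.

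**Cost.** Mostly protocol wording, with four practical burdens:

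- Clips must be de-identified: Section 9.1 codes data and scoresheets, not images.
- The second reader takes on ROI placement, where Section 5 plans only a second interpretation.
- Whoever scores image quality at the scan, so that the image-futility rule in Section 8.8 is not delayed, should not be the masked reader for that infant.
- Masking will be incomplete where signs such as pneumatosis are visible on the clip. The common ROI rule limits that part but does not remove it.

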### **3.3 Duration of Study Participation**

The study duration per subject will be approximately 20 minutes including the time to prepare Lumason™ contrast agent, perform the pre-contrast imaging, and perform the CEUS, as well as the 60 minute monitoring period after the first and second injection of Lumason™. CEUS will be performed at the time of suspected or diagnosed NEC, a second CEUS may be performed, and at the time of surgery (for subjects undergoing surgery as part of clinical care) or at short-term follow-up of clinical condition (approximately within 1-2 weeks from the first scan) for a total of two CEUS exams of 1 hour and 20-minute duration each.

Study participation will be complete when the 60 minute monitoring period after the last CEUS performed is complete (after the first CEUS in patients who undergo one exam, or after the second CEUS is complete in patients who undergo two exams).

### **3.4 Total Number of Study Sites/Total Number of Subjects Projected**

The study will be conducted at one site, The Children's Hospital of Philadelphia. It is expected 200 subjects will be enrolled to produce 100 evaluable subjects.

### **3.5 Study Population**

#### **3.5.1 Inclusion Criteria**

1. Males and females aged 1.5 years or younger
2. Post menstrual age of 29 weeks or older

3. Patients with suspected or diagnosed necrotizing enterocolitis
4. Patient in the CHOP NICU or PICU
5. Parental permission

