0.03 mL/kg may provide more optimal imaging results. Therefore, the study team proposes that a dose range of 0.01-0.03 mL/kg be considered for dose optimization of the initial subjects, as indicated. Based on the published report of safe infusion of the investigational drug in four premature infants from 26.9 to 29.5 weeks gestational age [15] as well as 3 additional premature subjects from unpublished data of the sponsor, this dose range seems appropriate. For each subject, the dose per injection, as well as the total dose delivered, will be recorded in the study file for each administration of study drug. The expectation is that the intravenous injection of this ultrasound contrast agent will permit noninvasive, non-ionizing delineation of physiology and pathophysiology with higher resolution and accuracy than conventional ultrasound techniques. Since preliminary studies at Hopkins showed that half of neonates required two injections of contrast agent to achieve evaluable CEUS images, two injections will be performed per CEUS scan in all subjects to ensure adequate image quality and reproducibility.

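### The NEC-versus-normal comparison is an unadjusted Wilcoxon test between groups formed by diagnosis over a wide age range; adjusting for recorded age would protect against bias that can raise false positives or cost power.

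*Combined protocol and SAP*

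**What the plan says.** Section 6 sets the quantitative comparison: region-of-interest measurements are compared with those of control subjects, defined as "those with suspected or at risk of necrotizing enterocolitis but turns out to be normal on imaging and clinical evaluation", and the comparison is made "using non-parametric Wilcoxon testing". Section 6.1 and the Synopsis make NEC versus normal the primary endpoint. Section 3.2 answers the question of allocation with "Not applicable. The CEUS scan will be interpreted by the sponsor-investigator only".

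No part of Section 6 names a covariate, matching, stratification or a sensitivity analysis. Section 6.3.1 gives baseline data a descriptive summary only.

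The population is wide. Section 3.5.1 admits infants with "Post menstrual age of 29 weeks or older", up to 1.5 years of age, from the NICU or PICU. Section 7.1 expects up to about 10 kg at one year.

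The likely covariates are largely in hand. Section 4.5.2 lists date of birth and weight, and Section 7.2 records the dose per injection for each subject. The same section proposes that "a dose range of 0.01-0.03 mL/kg be considered for dose optimization of the initial subjects".

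**The concern.** A two-sample Wilcoxon test gives a valid test of an NEC effect only if the groups would have had the same distribution of perfusion without NEC. Randomisation would secure that; grouping by final diagnosis does not.

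The documents give some reason not to assume balance. The Synopsis and Section 1.1 put NEC at 1-5% of NICU admissions but up to 10% of neonates under 1500 g, so diagnosis tracks size in the general NICU population. Section 6.4 says contrast ultrasound quantifies by absolute intensity, and Section 5 lists peak intensity and area under the curve among the measures. These could plausibly vary with maturity or size.

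At stake is the meaning of the primary result. A significant difference could partly reflect age, and a real difference could be masked by it.

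**Working it through.** **Inputs from the documents.** 40 per group, Cohen's d 0.71, alpha 0.05 and stated power 0.88 (Section 6.4).

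**Inputs assumed, because the documents give neither.** The within-group correlation rho between covariate and perfusion (0, 0.3, 0.5), and the difference in covariate means between groups, in SD units (0 to 0.8).

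**Step 1: reproduce the plan's figure.** For two independent groups the noncentrality is d × √(n/2) = 0.71 × √20 = 3.175. The two-sided normal approximation gives P(Z > 1.96 − 3.175) = 0.888, and the two-sided t-test gives 0.880. The plan's 0.88 is therefore an unadjusted, two-sided comparison of two independent groups. For the Wilcoxon test actually planned (asymptotic relative efficiency 0.955), power is about 0.865. A paired t-test with 40 pairs and the same standardised effect would give 0.992, so the stated figure is not a within-subject calculation.

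**Step 2: false positives.** With no NEC effect, the covariate alone shifts the groups apart by rho × imbalance. For rho 0.5 and 0.5 SD the shift is 0.25 SD. The Wilcoxon noncentrality is 0.25 × √20 × √0.955 = 1.093, and the rejection rate is P(Z > 0.867) + P(Z < −3.053) = 0.194. Simulation (10,000 runs for most scenarios) gives 0.19, which agrees. Simulated type I error at nominal 0.05:

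| Imbalance | Wilcoxon, rho 0.3 | Wilcoxon, rho 0.5 | Rank ANCOVA |
|---|---|---|---|
| 0 | 0.05 | 0.05 | 0.05 |
| 0.25 SD | 0.06 | 0.08 | about 0.05 |
| 0.5 SD | 0.10 | 0.19 | about 0.05 |
| 0.75 SD | 0.15-0.16 | 0.37 | about 0.05 |

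With rho = 0 the Wilcoxon test stays at about 0.05 whatever the imbalance.

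**Step 3: power at d = 0.71.**

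| Scenario | Wilcoxon | Rank ANCOVA |
|---|---|---|
| Balanced, rho 0.3 / 0.5 | 0.86 / 0.86 | 0.89 / 0.93 |
| 0.5 SD opposing NEC effect, rho 0.3 / 0.5 | 0.67 / 0.51 | 0.86 / 0.91 |
| 0.5 SD reinforcing NEC effect, rho 0.3 / 0.5 | 0.95 / 0.98 | 0.87 / 0.93 |
| 0.75 SD, rho 0 | 0.87 | 0.81 |

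In the third row the Wilcoxon rejects more often because of bias, not because it is more sensitive.

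**Step 4: when adjustment gains precision.** In a linear model with 1:1 groups and one covariate, adjustment multiplies the variance of the group difference by (1 − R²) × (1 + imbalance²/4). Break-even is R² = 1 − 1/(1 + imbalance²/4). At 0.5 SD this is 1 − 1/1.0625 = 5.9%, and at 0.8 SD it is 1 − 1/1.16 = 13.8%. A correlation of 0.3 gives R² = 9% and a correlation of 0.5 gives 25%.

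**The case against.** The strongest objection is that the harm is hypothetical. The documents report no association of age, weight or dose with perfusion and no expected imbalance. Both groups come from one source, ICU infants suspected of, at risk of or diagnosed with NEC (Section 3.1.1), which should limit imbalance. This stands. It is why the figures are conditional and why the 0.25 SD row matters as much as the larger ones.

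A reader might infer that false positives will rise and power will be lost. The documents do not support that. At zero correlation or zero imbalance the Wilcoxon test is sound. If the imbalance reinforces the NEC effect, apparent power rises. Adjusting for an imbalanced but irrelevant covariate costs power.

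A reader might also infer that the threefold dose range is a major confounder. That is not supported either. Section 7.2 proposes the range for the initial subjects only and conditionally, and nothing links dose to diagnosis. Assume 10 of 80 subjects receive a reduced dose and that intensity scales with dose. Type I error is then 0.04 if they split 5/5 between groups and 0.05 if 7/3. It reaches 0.09-0.20 only if all 10 have NEC. Dosing per kilogram also handles weight in part.

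The covariates are not entirely free of new work: Section 4.5.2 does not list gestational age, which post-menstrual age at scan requires. Section 3.5.1 needs post-menstrual age for eligibility, but no section says it is kept for analysis.

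Age and weight are probably collinear, but a three-covariate model with collinear age and weight also held type I error at about 0.05 in simulation.

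Two defences do not succeed. The statement in Section 6.4 that each subject is its own control concerns clinical ultrasound versus CEUS, not NEC versus normal infants. The feasibility framing does not remove the issue, because the plan names a between-group test and powers it.

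**Conclusion.** The concern holds in conditional form. The defect is in the analysis sentence of Section 6; the inclusion criterion shows only how wide the age range is. The primary quantitative comparison leaves recorded age and size unused in groups that were not randomised.

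Under assumed correlations of 0.3 to 0.5, the false-positive rate is 0.06-0.08 at a small imbalance (0.25 SD), 0.10-0.19 at 0.5 SD and 0.15-0.37 at 0.75 SD. The adjusted test stays near 0.05. Power is at risk when the imbalance opposes the NEC effect. These figures assume 40 per group, a linear relation and a covariate measured without error. Confounding by factors that are not recorded would remain after adjustment.

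Confidence is moderate, and the change is best seen as a cheap improvement.

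**What to change.** In Section 6, replace the Wilcoxon test as the primary quantitative comparison with a rank-based ANCOVA: regress the ranked perfusion measure on group and age at scan. Use post-menstrual age where gestational age is available, otherwise age from date of birth. Add weight only if it is not redundant with age. Keep the unadjusted Wilcoxon test as supportive. State the covariates before results are seen.

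If doses vary, add the recorded dose per kilogram as a covariate in a sensitivity analysis. Before that, Section 3.1.2, which gives the dose in mg/kg, must be reconciled with Sections 1.2, 7.1 and 7.2, which give it in mL/kg.

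The cost is revised wording and minor analysis work. Keeping gestational age in the study record would be a small addition if it is not already stored. The statistical price is some loss of power if the covariate is imbalanced but unrelated to perfusion, for example from about 0.87 to 0.81 at 0.75 SD.
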